4.3 Handling of repeated and unscheduled measurements

All repeated and unscheduled measurements will be presented in the listings. The following general rules will apply to all repeated and unscheduled measurements:

- For repeated measurements obtained prior to the first dose of IMP the latest value (which may be scheduled or unscheduled) will be used in the calculation of descriptive statistics
- For repeated measurements obtained at the designated Baseline visit, the latest value (which may be scheduled or unscheduled) will be defined as the Baseline provided that this occurred prior to the first dose of IMP. Repeated measurements designated Baseline will be used in descriptive statistics rather than the planned measurement they replace
- For repeated measurements obtained at any time point after the first dose of IMP, the first value of any repeated measurements will be used in the calculation of changes from Baseline and for the descriptive statistics. Unscheduled and repeated measurements will not be included in the descriptive statistics at time points after the first dose of IMP

The above rules also apply to triplicate measurements obtained for the ECG data, both for repetitions of the whole triplicate or when single measurements of the triplicate are repeated.

4.4 Interim analyses and data monitoring

At least three interim analyses will be performed. The first interim analysis for futility will be performed once approximately 20 subjects have attended Visit 9, the first visit of the second Dosing Period (ie, Day 29). Futility of UCB7665 will be assessed based on QMG score, MG-Composite score, and MGADL data. In case of futility, the study will be stopped or amended. The decision rules for futility will be described in the data monitoring committee (DMC) charter. The second interim analysis will be conducted after approximately 20 subjects (receiving 6 sc infusions) have had Visit 16 (Day 57). Based on this unblinded analysis the safety of UCB7665 will be assessed by the DMC. The safety variables to be used and the potential outcomes of the analysis will be specified in the DMC charter. During this review recruitment will not be stopped. The third interim analysis will be performed once all subjects have attended Visit 9 (Day 29), the first visit of the second Dosing Period (ie, Day 29). This interim analysis will provide the results for the primary variable 'change from Baseline to Visit 9 (Day 29) in the QMG score', and secondary variables 'change from Baseline to Visit 9 (Day 29) in MG-Composite score' and 'change from Baseline to Visit 9 (Day 29) in the MGADL score'. For the third interim analysis the DMC will not be utilized.

The analyses will be described in a separate Interim SAP. The first interim analysis will utilize all efficacy data (as specified in the DMC charter), which will be available at the time the 20th subject attended Visit 9. The second interim analysis will utilize all safety data (as specified in the DMC charter), which will be available at the time the 20th subject attended Visit 16. For all interim analyses, the data subject to analysis should be as clean as possible; however, the database will not be locked and a snapshot will be taken.

4.5 Multicenter studies

Individual center results will not be displayed.

4.6 Multiple comparisons/multiplicity

Not applicable

4.7 Use of an efficacy subset of subjects

Not applicable

4.8 Active-control studies intended to show equivalence

Not applicable

4.9 Examination of subgroups

Not applicable

5 STUDY POPULATION CHARACTERISTICS

5.1 Subject disposition

The number of subjects who were enrolled, dosed, subjects included in each analysis set, and subjects who completed or prematurely discontinued the study/the period, as well as the reason

for discontinuation, discontinuation due to AEs, will be presented by dose arm and overall. Screen failure reasons will be summarized, based on the ES.

In addition the following listings will be presented by dose arm:

- Subject disposition (ES)
- Study discontinuation (ES)
- Visit dates (RS)
- Subject analysis sets (ES)

Subject disposition will be listed by treatment group based on the ES, and will include the date of informed consent, presence of informed consent for SFEMB with date, date of randomization for Dosing Period 1 and Dosing Period 2, date and time of first and last dose of IMP, date of premature termination and primary reason, and date of final contact.

The listing of study discontinuation will include the reason for discontinuation, period of discontinuation, with dose and number of days on that dose and the total number of days on study medication.

The number of days on IMP will be calculated as follows:

Number of days on IMP=[(Date of Last Dose Received)-(Date of First Dose Received)]+1

5.2 Protocol deviations

Important protocol deviations (IPDs) will be identified and classified by the deviation types identified in the IPD document. A listing of all IPDs identified at the Data evaluation meetings (DEMs) will be presented for all subjects in the SS, and will include the deviation type and description. The number and percentage of subjects in the SS with IPDs will be summarized overall if appropriate. The denominator for percentages will be the number of subjects in the SS.

6 DEMOGRAPHICS AND OTHER BASELINE CHARACTERISTICS

6.1 Demographics

A by-subject listing of Baseline demographics will be presented by treatment group for the ES. This will include the day, month and year of birth (if available), age (in years), sex, race, ethnicity, height (in cm), weight (in kg) and body mass index (BMI). The age will be directly entered into the study database and will not be re-calculated for the statistical analysis. Childbearing potential will be listed for the ES.

All demographic characteristics obtained at the Screening visit will be summarized for the RS (apart from the date of birth).

Body mass index in kg/m² is calculated based on the height (in m) and the weight (in kg) using the following formula:

$$\text{BMI (kg/m}^2\text{)} = \text{weight (kg)} / [\text{height (m)}]^2$$

The BMI will be reported to 1 decimal place.

The demographic characteristics listing will include a flag for BMI values identified as TEMA/PCS as defined by the criteria outlined in [Table 14-7](#).

For the EudraCT reporting, the age categories will include

- 18 to <65 years
- 65 to <85 years
- ≥85 years

For the clinicaltrials.gov reporting, the age categories will include:

- ≤18 years
- 19 to <65 years
- ≥65 years

6.2 Other Baseline characteristics

MG medication (medication where indication is MG), MGFA disease class and thymectomy (yes/no) at baseline will be listed and summarized by treatment group for the RS.

6.3 Medical history and concomitant diseases

Medical history will be listed and summarized for the RS by treatment group, and will include the MedDRA system organ class (SOC), high level term (HLT) and preferred term (PT). Procedure history and concomitant medical procedure will be listed separately from the medical history based on the RS.

History of MG will be listed for the RS.

6.4 Past, prior and concomitant medications

Past, prior and concomitant medications will be listed and summarized, separately, for the RS by treatment group and for all subjects by WHODD Anatomical Main Group [Level 1], Therapeutic Subgroup [Level 3], preferred term (PT) and reported term (listing only). The listing will also include the dose per intake and unit, frequency, formulation, route of administration, indication, category (three categories; prior, concomitant and prior and concomitant), study period (Dosing Period 1, Dosing Period 2 and/or Observation Period) and both start and end date (or ongoing, if applicable).

Separate tabulations will be presented for the following:

- Past medications
- Prior and concomitant medications
- Concomitant medications

All medications will be listed and will include coding information, reported term, dose per intake and unit, frequency, formulation, route of administration, indication, category (past/prior and concomitant/concomitant) and start and end date (or ongoing, if applicable).

6.4.1 Past medication definition

Past medications will include any medications that started and stopped prior to the first IMP administration.

6.4.2 Prior medication definition

Prior medications will include any medications that started prior to the first administration of IMP. This includes any medications that started and stopped prior to dosing (past medications) as well as those which started prior to dosing and continued after (classified as prior and concomitant medications).

6.4.3 Concomitant medication definition

Concomitant medications will include any medication that has been taken at least once (after the first administration of IMP) during the Dosing Periods and/or the Observation Period.

Any medication that started prior to the first administration of IMP and continued after dosing will be classified as prior and concomitant. Any medication that started after the first administration of IMP in Dosing Period 1 will be classified as concomitant only.

Any medications with missing dates and/or times will be handled as described in [Section 4.2.7](#) in order to classify them as prior or concomitant.

6.4.4 Assignment of medications to study period

The following rules will be used to assign a concomitant medication to a study period:

- Dosing Period 1: a medication will be assigned to Dosing Period 1 if it has been taken at least once between the first administration of IMP on Day 1 and the first administration of IMP in Dosing Period 2 (Day 29). This includes medications that started prior to Dosing Period 1 and those that continued into Dosing Period 2.
- Dosing Period 2: a medication will be assigned to Dosing Period 2 if it has been taken at least once between the first administration of IMP in Dosing Period 2 (Day 29 and 7 days after the last dose of IMP in Dosing Period 2 [Day 50]). This includes medications that started prior to Dosing Period 2 and those that continued into the Observation Period.
- Observation Period: a medication will be assigned to the Observation Period if it has been taken at least once between Day 50 (or 7 days after the last dose of IMP) and the final visit. This includes medications that started prior to the Observation Period.

Thus, a medication taken from the time of the first drug administration in Dosing Period 1 to the end of the study will be assigned to Dosing Period 1, Dosing Period 2 and the Observation Period.

7 MEASUREMENTS OF TREATMENT COMPLIANCE

The study medication will be administered and monitored by the investigator or designee. The measured plasma concentrations will provide information regarding compliance. Any dosing deviations (eg, incomplete infusion volume administered, infusion temporarily interrupted, infusion discontinued) will be discussed at the DEM and any actions taken regarding the analyses will be documented accordingly and discussed in the CSR.

There will be no specific analysis of compliance. Exposure to UCB7665 will be presented as described in [Section 11.1](#).

8 EFFICACY ANALYSES

8.1 Statistical analysis of the primary efficacy variable

The primary efficacy variable is the change from Baseline in QMG score to Visit 9 (Day 29) prior to the first infusion of IMP in Dosing Period 2.

8.1.1 Derivations of primary efficacy variable

The QMG scale comprises 13 items, including ocular and facial movement, swallowing, speech, limb strength and forced vital capacity. Scoring for each item ranges from no weakness (0) to severe weakness (3), with an overall score range from 0 to 39, ie, a higher scores indicates more severe disease. A 3-point change in the overall score is considered to be clinically relevant.

The complete list of items and scores are provided in [Table 14–1](#). The items of QMG scale will be displayed in a glossary. A total score after single item imputation will be calculated according to the rules set down in [Section 14.1](#). All individual item results will be listed. The total score after single item imputation will be listed and used to calculate change from baseline, in descriptive summaries and for efficacy analysis. Total score will be used to determine responder state, which will be flagged in the listing and descriptively summarized.

8.1.2 Primary analysis of the primary efficacy variable

A 1-sided hypothesis test will be performed to test the primary hypothesis of superiority of UCB7665 7mg/kg vs placebo at Visit 9. The null hypothesis is that the mean change from Baseline in QMG score is larger or equal in the UCB7665 7mg/kg group than the placebo group. The alternative hypothesis is that the mean change from Baseline in QMG score is smaller in the UCB7665 7mg/kg group than the placebo group.

The primary analysis of the primary variable will be analyzed for the FAS using a mixed model repeated measures (MMRM) analysis of covariance (ANCOVA) that includes terms for week (as categorical effect), treatment group, the Baseline QMG score, and the interaction between treatment group and week. The model will define subject as a random effect and utilize an unstructured covariance pattern. Least Squares (LS) Means for changes from Baseline at Visit 9 (Day 29) for each treatment group will be presented together with LS mean differences (UCB7665 - 7mg/kg vs placebo), p-value and 1 sided 95% CI.

For subjects who prematurely withdraw for any reason before Visit 9 (Day 29), data collected during the PEOT Visit will be used to impute QMG scores at the next consecutive visit.

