Although the prognosis of MG has markedly improved over the last decades, with new therapies dramatically improving survival, significant mortality and even morbidity remains an issue. Treatment of MG remains a difficult clinical problem, requiring the long-term use of high-dose corticosteroids alone or combined with cytotoxic agents. Many of the therapies thought to be effective in MG have insufficient data to clearly support their use, are not effective in all patients and conditions, and have broad immunosuppressive effects causing considerable toxicity and treatment-related morbidity. Moreover, due to the natural fluctuations in the course of the disease, many patients need an effective treatment for acute situations requiring urgent treatment. Both PLEX and IVIg currently are used as the standard of care to improve symptoms in situations requiring chronic-intermittent treatment; however, neither treatment is approved in the US for MG, and the procedures often are burdensome for the patients. Thus a significant unmet medical need exists in this patient population for an effective chronic-intermittent treatment with increased convenience for patients with generalized MG.

UCB7665 is being developed as an inhibitor of FcRn activity with the aim to reduce the concentration of pathogenic IgG in patients with IgG autoantibody mediated diseases. UCB7665 was derived from a rat antibody with specificity for human FcRn.

Both preclinical studies in nonhuman primates and clinical studies suggest that treatment with UCB7665 may reduce the concentration of pathogenic IgG. The relationship between UCB7665 exposure and the primary PD effect on plasma IgG levels was studied in Cynomolgus monkeys

following single- and repeat dose administrations by both intravenous (iv) and sc routes. UCB7665 mediated a clear dose- and exposure-related decrease in plasma IgG concentrations, achieving 45% to \geq 70% decreased IgG concentrations at dose levels ranging from 5 to 30mg/kg in the absence of adverse effects. No consistent or dose-related effects of UCB7665 on albumin levels were observed in these studies.

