In summary, the genetic, epigenetic, and genomic elements of MG require further elucidation to understand the cause, progression, and appropriate treatment of MG. Through the voluntary collection of blood DNA and RNA samples from consenting subjects, this substudy will help enable further investigation of this complex disease. This documen

6

prior to

SELECTION AND WITHDRAWAL OF SUBJECTS

6.1 **Inclusion criteria**

To be eligible to participate in this study, all of the following criteria must be met:

- variations thereof 1. An Institutional Review Board (IRB)/Independent Ethics Committee (IEC) approved written Informed Consent form is signed and dated by the subject.
- 2. Subject is ≥ 18 years of age at Visit 1 (Screening).
- 3. Subject has a well-documented diagnosis of MG at Visit 1 (Screening), based on subject history and supported by previous evaluations. 5
- 4. Subject would currently be considered for treatment with immunological therapy (eg IVIG/PLEX) by the investigator.
- 5. Subject has a well-documented record of autoantibodies against or Visit 1 (Screening).
- 6. Female subjects of child bearing potential must have a negative serum pregnancy test at the Screening Visit, which is confirmed to be negative by urine testing prior to the first dose of study drug at Week 1 (Visit 2) and prior to further dosing at each study visit thereafter.

Female subjects of childbearing potential must agree to use a highly effective method of birth control, during the study and for a period 2 months after their final dose of study drug. According to the International Council for Harmonisation (ICH) M3 (R2), highly effective forms of birth control are methods which achieve a failure rate of less than 1% per year when used consistently and correctly. Highly effective methods of birth control include:

- Combined (estrogen- and progesterone-containing) hormonal contraception (oral, implant, injectable) associated with inhibition of ovulation, (which must be stable for at least 1 full month prior to Screening [Visit 1], and should remain stable during the study).
- Progesterone-only hormonal contraceptives (oral, implant, injectable) associated with inhibition of ovulation (which must be stable for at least 1 full month prior to Screening [Visit 1], and should remain stable during the study).
- Progesterone-releasing intrauterine systems or the TCu 380A intrauterine device.

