6.4 Withdrawal criteria

Subjects are free to withdraw from the study at any time, without prejudice to their continued care.

Subjects MUST be withdrawn from the study if any of the following events occur:

- 1. Subject withdraws his/her consent.
- 2. Subject becomes pregnant during the study, as confirmed by a positive pregnancy test.

Subjects MUST discontinue IMP if any of the following events occur:

- Atiations thereof 1. Subject develops an illness or has a change in health status that would interfere with his/her continued participation, including but not limited to:
 - Subject has a serious infective episode requiring hospitalization or iv antibiotic therapy (including but not limited to bacteremia or sepsis, bacterial meningitis, osteomyelitis or septic arthritis, bacterial pneumonia, or visceral abscess).
 - Subject experiences a severe adverse event (AE) of GI disturbance or severe headache which is considered related to the IMP in the opinion of the investigator (Section 12.1.10).
 - Subject has an AE of infusion reaction of severe intensity requiring corticosteroid and/or epinephrine therapy.
 - Subject has an AE of anaphylactic reaction requiring corticosteroid and/or epinephrine therapy.
 - Subject has a TB test that is confirmed positive or any further evidence suggestive of potential TB infection (eg, exposure) and further examinations result in a diagnosis of active TB or LTBI (refer to Section 12.3.1) for further details and instructions.
 - If an NTMBI is identified during a study, the same withdrawal procedures as those _ used for an active TB infection identified during the study should be followed.
- 2. The sponsor or a regulatory agency requests withdrawal of the subject.
- 3. Subject is treated with rescue therapy (refer to Section 7.8.3).
- 4. Subject received rituximab during the Treatment Period.
- 5. Subject received prohibited concomitant medications (as defined in Section 7.8.2 of this protocol) during the Treatment Period.
- 6. According to the investigator's judgment this is in the best interest of the patient.
- 7. Meets criteria for liver injury (Section 6.4.1).
- 8. Subject has active suicidal ideation as indicated by a positive response (Yes) to either Question 4 or Question 5 of the "Since Last Visit" version of the C-SSRS. The subject should be referred immediately to a Mental Healthcare Professional.

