7.8.2 Prohibited concomitant treatments (medications and therapies)

The following concomitant medications and therapies are prohibited during the study:

- IVIg ٠
- All biologics including rituximab ٠
- Cyclophosphamide •
- Pimecrolimus •
- IPP-201101 (LupuzorTM) •
- PLEX •
- Immunoadsorption .
- Janvertensions or variations thereof. Janvertensions or variations thereof. Medications which could interfere with the function of the NMJ (and which therefore could impair subjects with MG), such as, but not limited to, the following medications. For a more REDACTED Authoritation detailed list please refer to the MGFA medication list (http://www.myasthenia.org/LivingwithMG/DrugstoAvoid.aspx).
 - botulinum toxin
 - aminoglycoside antibiotics
 - tetracycline antibiotics
 - penicillamine

If a subject needs or takes any prohibited medication or therapy (except IVIg, PLEX, or rituximab), the investigator will (where possible) discuss with the sponsor study physician and a decision will be made whether the subject can continue in the study or must be withdrawn. If the subject is treated with IVIg, rituximab, or PLEX, the subject must be withdrawn from the IMP, but should be encouraged to continue with Observation Period Visits.

For subjects who require a medical or surgical procedure that requires the use of general anesthesia, discussion must occur prior to the procedure with the medical monitor or study physician. In an emergency situation, discussion should occur as soon as possible after the procedure, such that a decision on the subject's continued participation in the study can be made.

Rescue medication 7.8.3

In the case of prolonged hypogammaglobulinemia the subject will be considered for treatment with prophylactic antimicrobial therapy. Subjects will be followed up until Ig levels return to within the normal range.

Aff, during the Treatment and Observation Period, in the opinion of the investigator, a subject has a significant deterioration in clinical condition, then rescue therapy such as IVIg or PLEX should be considered.

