8.1.3 Supportive and sensitivity analyses of the primary efficacy variable

Different sensitivity analyses to evaluate the effect of missing observations on the primary analysis findings will be done. The first sensitivity analysis will be performed in the same way as the primary analysis but will use PPS instead. A further analysis will utilize the Last Observation Carried Forward (LOCF) approach and the FAS; missing values will be replaced by the last observed post-Baseline value of the variable and the analysis will be performed on the resulting dataset.

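### The SAP has no rule for scores taken after rescue IVIg or PLEX, so they can enter the FAS analyses, be carried to Visit 9 by LOCF and count as response

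*SAP*

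**What the plan says.** **Rescue.** Protocol 7.8.3 says that if a subject deteriorates significantly in the Treatment or Observation Period, "then rescue therapy such as IVIg or PLEX should be considered". Protocol 6.4 makes treatment with rescue a mandatory reason to stop study drug. Protocol 7.8.2 adds that a subject given IVIg or PLEX must be "withdrawn from the IMP, but should be encouraged to continue with Observation Period Visits".

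**PEOT Visit.** Protocol 8.5 schedules it as near as possible to the withdrawal decision, with the same assessments as the Final Visit. Protocol 8.4.6 shows that these include QMG, MG-Composite and MGADL.

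**Analysis.**
- SAP 8.1.2 (QMG): "For subjects who prematurely withdraw for any reason before Visit 9 (Day 29), data collected during the PEOT Visit will be used" to fill the next visit. SAP 8.2.1 repeats the rule for MG-Composite, and 8.3.2, 8.3.3 and 8.3.5 repeat it for other scales. SAP 3.2.3 maps PEOT efficacy data to the next scheduled visit in general.
- SAP 8.1.3, LOCF on the FAS: "missing values will be replaced by the last observed post-Baseline value of the variable".
- SAP 8.1.1 derives responder status from the total score. SAP 8.3.6 compares responder rates by Fisher's exact test in Dosing Period 1.
- SAP 8.2.2 analyses MGADL by ANCOVA in subjects with Baseline and Visit 9 values.
- SAP 3.5.4 defines the FAS by dosing and QMG availability. SAP 3.5.5 allows specific data to be dropped from the PPS after an important deviation.

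The SAP never mentions rescue.

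**The concern.** Protocol Section 2 describes the rescue therapies as effective: "Both PLEX and IVIg currently are used as the standard of care to improve symptoms". Inclusion criterion 4 in Protocol 6.1 makes every participant a current candidate for them: "Subject would currently be considered for treatment with immunological therapy (eg IVIG/PLEX) by the investigator". A score taken after rescue may therefore reflect the rescue and not the assigned arm.

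As written, such a score is treated like any other. It can stand at Visit 9 in the LOCF analysis, inform Visit 9 in the MMRM, and turn a treatment failure into a responder. With about 20 evaluable subjects per arm, one or two such subjects can be visible in the result. The plan also does not say whether keeping these scores is a deliberate treatment-policy choice or an omission.

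**Working it through.** **The plan's own figure.** The sample size sections claim more than 90% power, but the SD, effect, alpha and dropout allowance are redacted. The figure cannot be reproduced and is not in dispute here.

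**Step 1. Does the PEOT score follow rescue?** The stopping criterion is that the subject has been treated with rescue, so a stop for that reason comes after it. The visit is held close to the decision, so it may precede any rescue effect. The post-rescue gap could therefore be near zero.

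**Step 2. Where does the score go?** QMG is scheduled in this stretch at Visits 2, 4, 6, 8 and 9 (Days 1, 8, 15, 22 and 29).

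| PEOT falls | Visit filled | Visit 9 in primary MMRM | Visit 9 in LOCF |
|---|---|---|---|
| between Visits 2 and 4 | 4 | indirect, through the covariance | copied if no later score exists |
| between Visits 4 and 6 | 6 | same | same |
| between Visits 6 and 8 | 8 | same | same |
| between Visits 8 and 9 | 9 | direct | already at Visit 9 |

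There is a second route. SAP 3.2.2 treats data up to a missed first dose of Dosing Period 2 according to plan. After a rescue following the third dose (Day 15), any scores actually collected at Visits 8 and 9 also enter.

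**Step 3. Size in the LOCF analysis.** Inputs:
- 20 per arm, from 40 evaluable subjects at 1:1 (Protocol 5.1 and 5.1.3).
- Gap g between a subject's last pre-rescue score and the post-rescue score: not in the documents, assumed 4 to 8 points.

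Shift of the raw arm mean per rescued subject = g / 20.
- g = 4: 4 / 20 = 0.2 points
- g = 8: 8 / 20 = 0.4 points

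Against the 3-point change that Protocol 9.1 calls clinically relevant, that is 0.2 / 3 = 7% to 0.4 / 3 = 13% per subject. A rescued placebo subject moves the difference towards zero; a rescued active-arm subject moves it away from zero by the same amount.

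**Step 4. Size in the primary MMRM.** If the score maps to Visit 9, it is one of about 20 observed values there. If it maps earlier, its influence is only through the covariance and is smaller. With no rescue in Dosing Period 1 it is nil.

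**Step 5. Responders.** Response needs at least 3 points of improvement from Baseline. A subject who had worsened by w points needs a rescue gain of at least w + 3. Each one who qualifies adds 1 / 20 = 5 percentage points to that arm. As an example, 10/20 against 4/20 gives a one-sided Fisher p of 0.048; 10/20 against 5/20 gives 0.095.

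**The case against.** Several points on the other side are sound.

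- **The primary analysis.** A reader might infer that the primary MMRM carries post-rescue scores to Visit 9. It does not: the PEOT score fills one visit only. Carry-forward belongs to the LOCF sensitivity analysis for QMG, and then only when Visit 9 is missing. Earlier scheduled scores stay in the model.
- **Direction.** It is tempting to say that the contamination falls on placebo. That assumes the drug works. If it does, the bias is conservative for a superiority test; if rescue falls on the active arm, the direction reverses. The documents do not settle this.
- **Frequency and effect.** No rescue rate is given. Exclusion criterion 6 removes subjects with severe bulbar or respiratory weakness or with crisis. A large gain at a visit held close to the rescue decision is an assumption.
- **Per-protocol check.** IVIg and PLEX are prohibited treatments, and the PPS may drop affected data. This helps, but it is discretionary, does not name rescue and leaves the FAS unchanged. The deviation criteria sit in a separate document.
- **Observation Period.** One might read the summaries as crediting all rescued subjects to the drug sequences. SAP 3.1 and 3.6 show subjects with no Dosing Period 2 dose in separate groups. Only those rescued after receiving a Dosing Period 2 dose remain in the four sequence groups.
- **Treatment policy.** Keeping post-rescue scores can be a legitimate primary strategy. The plan does not say that it has chosen it.

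What remains is that stated FAS rules admit post-rescue scores without comment and can record a treatment failure as a success.

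**Conclusion.** The point holds as a cheap improvement to the SAP. The route from rescue to the FAS analyses follows from the text of both documents, and nothing in them closes it. The size is illustrative only: 0.2 to 0.4 points in one arm's LOCF Visit 9 mean per affected subject, given 20 per arm and an assumed gap of 4 to 8 points. For the primary MMRM the effect is smaller when the score lands before Visit 9, and nil without rescue in Dosing Period 1.

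The documents do not support the stronger conclusions that the primary result is biased by a known amount or direction, or that a rescue-censored analysis has to become primary. The choice of primary strategy is the sponsor's trade-off, but it should be stated.

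**What to change.** 1. Derive a first-rescue date from the concomitant medication and procedure records. Name the therapies that count, because Protocol 7.8.3 gives examples and not a closed list. Add a rule for scores on the rescue day, because SAP 4.2.7 notes that medication times are not recorded.
2. SAP 8.3.6: count a subject as a non-responder from that date.
3. SAP 8.1.3, LOCF: carry forward the last pre-rescue score, and say what happens when the only post-Baseline score follows rescue.
4. Add a sensitivity MMRM for QMG and MG-Composite, and a matching ANCOVA for MGADL (8.2.2), with post-rescue scores set to missing, alongside the all-data analysis. Sections 8.2.1 and 8.2.2 currently rule out sensitivity analyses and need rewording.
5. State in 8.1.2 which strategy is primary.
6. Make 3.2.3 and 4.2.1 consistent with 8.1.2. At present 4.2.1 says missing overall scores are not imputed, while 8.1.2 imputes from the PEOT Visit.
7. Flag post-rescue values in the Observation Period summaries.

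The cost is SAP wording, one derived date and a few extra outputs. SAP 3.8 leaves procedures uncoded, so PLEX entries would need a text review. The rescue-censored MMRM relies on missing at random after deterioration, which is why the all-data analysis stays beside it. No change to the clinical rescue rule is proposed.
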